# 5.4 Contraception

Female subjects of childbearing potential must use a highly effective method of contraception to prevent pregnancy for 4 weeks before randomization and must agree to continue strict contraception for 90 days after the last administration of IMP.

For the purposes of this trial, women of child bearing potential (WOCBP) are defined as "All female subjects after puberty unless they are post-menopausal (defined as amenorrhea for 12 months with documented date of last monthly period) or are surgically sterile (i.e., bilateral tubal occlusion)." For female subjects aged <55 who are considered post-menopausal and who are not on concomitant estrogen replacement therapy, confirmation of postmenopausal status will be required with follicle stimulating hormone (FSH) test results in the postmenopausal range for age at Screening (Visit 1).

Highly effective contraception is defined as methods which can achieve a failure rate of less than 1% per year when used consistently and correctly. Such methods include: combined (estrogen + progestogen) hormonal contraception (oral/intravaginal/transdermal); progestogen-only hormonal contraception (oral/injectable/implantable); intrauterine device (IUD); intrauterine hormone-releasing system (IUS); vasectomized partner (provided that partner is the sole sexual partner of the WOCBP study subject and that the vasectomized partner has received medical assessment of the surgical success); or sexual abstinence (defined as refraining from heterosexual intercourse from 4 weeks before randomization until 90 days after the last administration of IMP and only if this is the preferred and usual lifestyle of the subject).

WOCBP must have a negative serum pregnancy test at Screening (Visit 1) and a negative urine pregnancy test at baseline/Day 1 (Visit 2) before dosing.

Protocol No.: GSN000300	Compound No.: GKT137831
Protocol Version No.: Final 4.0; Amendment 3	Sponsor: Genkyotex
Protocol Date: 24 July 2018	Author: Cmed Clinical Services

Male participants with female partners of childbearing potential must be willing to use a condom and require their partner to use an additional form of adequate contraception as approved by the Investigator, such as an established form of hormonal contraceptive, a diaphragm or cervical/vault cap, IUD, or sponge with spermicide. This requirement begins at the time of informed consent and ends 90 days after last administration of IMP. Male study participants must also not donate sperm from baseline until 90 days after last administration of IMP.

# 5.5 Strategies for Recruitment, Retention and to Improve Adherence to Protocol

Sites will be selected based on their access to the PBC population. Several strategies may be implemented as enhancements to support subject identification and recruitment, including advertising through patient advocacy groups/networks, on Orphanet and other health-related social networks and early engagement with Key Opinion Leaders in each country to provide PBC expertise as well as physicians actively treating patients in the selected countries to encourage potential referrals.

Genkyotex's designated Clinical Research Organization (CRO), Cmed, will provide ongoing management of enrollment by regular review of site performance. Upon indication a site may benefit from further support, the site and the Clinical Research Associate (CRA) will partner to re-examine the current recruitment strategy.

# 5.6 Treatment Assignment Procedures

# 5.6.1 Randomization Procedures

This will be a double-blind, randomized, placebo-controlled, multicenter, parallel group phase 2 trial. Approximately 100 subjects will be randomized and allocated to placebo or one of the 2 active treatment arms, according to a 1:1:1 randomization ratio, stratified at study entry by disease severity defined as baseline serum GGT < 2.5 x ULN or  $\geq$  2.5 x ULN). Accordingly, approximately 33-34 subjects will be allocated to each of the 3 treatment arms.

A master reproducible randomization list will be produced by or under the responsibility of Cmed accounting for block size and stratification. The IWRS will assign a unique randomization number in ascending, sequential order (with associated treatment arm) to the subject, based on the predetermined randomization schedule. The system will assign the pre-determined blocks of randomization numbers for each stratification level to ensure similarly balanced treatment groups. Assignment will be in sequential order within blocks and stratification level. The investigator will enter the randomization number in the electronic case report form (eCRF).

# 5.6.2 Blinding Procedures

This is a double-blind study: the Sponsor, subjects, investigator staff, persons performing the assessments and data reviewers and statisticians will remain blinded to the identity of the study treatments.

Protocol No.: GSN000300	Compound No.: GKT137831
Protocol Version No.: Final 4.0; Amendment 3	Sponsor: Genkyotex
Protocol Date: 24 July 2018	Author: Cmed Clinical Services

The identity of the study treatments will be concealed by the use of IMPs which are all identical in packaging, labeling, schedule of administration, appearance and odor.

Randomization data will be kept strictly confidential, and will be accessible only to authorized personnel (e.g., unblinded pharmacist or authorized designee), until unblinding of the trial as described in the statistical analysis plan (SAP).

Unblinding will only occur for the following reasons:

- Subject emergencies (see Section 5.6.3)
- Scheduled and unscheduled safety reviews by the SMB (see Section 9.7)
- At the time of the interim analysis (see Section 10.3)
- At the conclusion of the study.

# 5.6.3 Emergency Breaking of Assigned Treatment Code

If an emergency unblinding becomes necessary, the Investigator should notify the Sponsor/Medical Monitor prior to unblinding, if possible, unless identification of the IMP is required for emergency therapeutic measures. The result of the code break should not be revealed to the Sponsor/Medical Monitor. Unblinding will be performed through the IWRS. The Investigator will access the IWRS to access the subject's treatment code. The Investigator may always, for urgent safety reasons, break the blind at any time during the conduct of the study. If the blind is broken, the date, time and reason must be recorded in the subject's eCRF and any associated AE report.

#### The unblinded treatment code must not be recorded in the eCRF.

# 5.6.4 Reasons for Withdrawal

Subjects will be informed that they have the right to withdraw from the study at any time, without prejudice to their medical care, and that they are not obliged to state their reasons. Any withdrawal must be fully documented in the eCRF, and should be followed up by the Investigator.

The Investigator may withdraw a subject at any time if this is considered to be in the subject's best interest.

A subject MUST be withdrawn for the following reasons:

- Pregnancy or breast feeding.
- A change in UDCA dose during the treatment period.
- Confirmed or suspected DILI, as defined in Section 6.3.1.
- Confirmed or suspected liver decompensation, defined as hepatic encephalopathy, gastrointestinal tract bleeding due to esophageal varices, or ascites.

- Confirmed Grade ≥ 2 severity anemia without documented alternative cause, as defined in Section 6.3.2.
- Grade 3 severity AE recurring or not resolving after a pre-defined interruption and resumption of IMP (see Section 6.3).
- Any Grade 4 severity AE.
- Subject's withdrawal of consent.

The subject MAY be also discontinued for the following reasons:

- Protocol violations, including non-compliance and loss to follow-up. ٠
- Safety reasons.
- Administrative reasons.
- Other: the subject was withdrawn for a reason other than those listed above, such as termination of the study by the Sponsor (see Section 5.6.6).

A subject will be considered to have completed the study when he/she completes the final assessment visit of the follow-up period, i.e., Week 28 (Visit 8).

# 5.6.5 Handling of Withdrawals

If the IMP is prematurely discontinued (i.e., before Week 24), the primary reason for discontinuation must be recorded in the appropriate section of the eCRF and all efforts must be made to complete and report the observations as thoroughly as possible. A premature end of treatment evaluation should be performed following the subject's withdrawal as described in Section 7.5, and recorded in the early termination eCRF page. A final follow-up visit should be performed within 4 weeks following the early termination visit, as described in Section 7.4.

If a subject fails to return for follow-up, attempts should be made to contact the subject to ensure the reason for not returning is not an AE. Likewise, if a subject decides to discontinue from the study, an attempt should be made to establish that the true reason is not an AE (bearing in mind subjects are not obliged to state their reasons). For subjects considered lost to follow-up, the eCRF must be completed up to the last visit performed.

Ongoing AEs should be followed up in accordance with the procedures described in Section 9.2.4.

Subjects who discontinue early will not be replaced.

# 5.6.6 Termination of Study

This study may be terminated at any time by the Sponsor because of safety concerns, ethical issues; plans to modify, suspend or discontinue the development of the IMP or serious and/or continued non-compliance with the protocol.

Protocol No.: GSN000300	Compound No.: GKT137831
Protocol Version No.: Final 4.0; Amendment 3	Sponsor: Genkyotex
Protocol Date: 24 July 2018	Author: Cmed Clinical Services

If the study is suspended or terminated, the Sponsor will promptly inform the Investigator, and will also inform the regulatory authorities of the suspension or termination of the study and the reason(s) for the action. The relevant Institutional Review Board/Independent Ethics Committee (IRB/IEC) will also be informed promptly and provided the reason(s) for the termination or suspension by the Sponsor or by the investigator/institution, as specified by the applicable regulatory requirement(s).

The Sponsor may at any time, at its sole discretion, discontinue a study center for various reasons, including, without limitation, the following:

- Failure of the Investigator to enroll subjects into the study at a reasonable rate.
- Failure of the Investigator to comply with applicable laws and/or pertinent regulations.
- Submission of knowingly false information from the research facility to the Sponsor, CRA, or regulatory authorities.
- Insufficient adherence to protocol requirements.

The Sponsor will issue a written notice to the Investigator, which will contain the reasons for taking such action. If the study center is terminated for non-compliance, the Sponsor will notify the appropriate regulatory authorities.

# **6** TREATMENT OF SUBJECTS

# 6.1 Identity of Study Treatment(s)

# 6.1.1 Description and Formulation

The description of IMP provided to each study center pharmacy is shown in Table 3.

 Table 3
 Description of Investigational Medicinal Products

Drug code	GKT137831	Placebo
Formulation	Micronized API formulated with excipients in capsules	Matching capsules containing only the excipients
Strength	100 mg	-
Route	Oral	Oral

GKT137831 capsules will contain 100 mg GKT137831 powder formulated with the following excipients per capsule: microcrystalline cellulose, Aerosil® (silicon dioxide), magnesium stearate and hard gelatin.

# 6.1.2 Packaging and Labeling

The IMP will be packed and labeled in accordance with applicable local regulatory requirements and applicable International Conference for Harmonization (ICH) Good Manufacturing Practice (GMP) and ICH Good Clinical Practice (GCP) guidelines, and to protect the blinded nature of this clinical study. The multi-language tear-off label will be adapted to the size of the IMP package and translated into the appropriate languages.

Child resistant 150 mL high-density polyethylene (HDPE) bottles with a tamper evident seal containing 70 capsules of either 100 mg GKT137831 capsules or matching placebo will be provided to the responsible pharmacist at the study center, who will dispense the bottles of IMP in cardboard packs for each subject, at each dispensing visit, in accordance with the Pharmacy Manual which will be developed according to ICH GCP guidelines and applicable local laws.

# 6.1.3 Storage and Stability

The IMP must be stored in a cool, dry, area at room temperature (between 15°C and 25°C). At the site IMP must be securely locked and stored with restricted access. Temperature should be controlled during shipment and during storage at study centers. The IMP must not be frozen or stored above 27°C.

Protocol No.: GSN000300	Compound No.: GKT137831
Protocol Version No.: Final 4.0; Amendment 3	Sponsor: Genkyotex
Protocol Date: 24 July 2018	Author: Cmed Clinical Services

# 6.2 Administration of Study Treatment(s)

At each dispensing visit, each subject will be given individual packs containing 2, 4 or 6 (depending on the visit) IMP bottles (70 capsules of 100 mg GKT137831 and/or matching placebo per bottle), in accordance with Table 4 and the Pharmacy Manual. Each subject will be given a sufficient supply of IMP to last until the next study visit, with some overage (up to 3 days).

	Visits	Vis	it 2	Visit 3		Visit 4		Visit 5		Visit 6		Visit 7
	Week	Base Da	eline/ y 1	2		6		12		18		24 (End of Treatment)
	IMP Bottles	Р	A	Р	A	Р	А	Р	А	Р	A	No dispensing
arm	Placebo	2	_	4	_	6	_	6	_	6	_	No dispensing
atment a	400 mg OD	1	1	2	2	3	3	3	3	3	3	No dispensing
Trea	400 mg BID	_	2	_	4	_	6	_	6	_	6	No dispensing

 Table 4
 Quantity of IMP Bottles Dispensed at Each Visit

P = Placebo; A = Active (GKT137831)

The IMP will be orally self-administered BID, once in the morning and once in the evening (aiming for a period of at least 10 hours between doses) with meals or up to 30 minutes after eating a meal.

On the day of the visit, study subjects should not self-administer the IMP as usual but instead should bring the IMP bottles to the clinic (used and unused, see Section 6.5) where he/she will be instructed to self-administer the morning dose after the required pre-dose blood samplings have been performed, fasted. The subject must fast overnight from 10 p.m.

The dose of test product will be 400 mg OD or 400 mg BID for 24 weeks.

Each day during the treatment period, subjects will self-administer 4 capsules in the morning and 4 capsules in the evening.

All subjects will be provided with:

- 2 bottles at baseline/Day 1 (Visit 2) and will self-administer:
  - When allocated to GKT137831 400 mg OD: 4 capsules of GKT137831 100 mg from one bottle in the morning and 4 capsules of placebo from the other bottle in the evening.

Protocol No.: GSN000300	Compound No.: GKT137831
Protocol Version No.: Final 4.0; Amendment 3	Sponsor: Genkyotex
Protocol Date: 24 July 2018	Author: Cmed Clinical Services

- When allocated to GKT137831 400 mg BID: 4 capsules of GKT137831 100 mg from one bottle in the morning and 4 capsules of GKT137831 100 mg from the other bottle in the evening.
- When allocated to placebo: 4 capsules of placebo from one bottle in the morning and 4 capsules of placebo from the other bottle in the evening
- 4 bottles at Week 2 (Visit 3) and will self-administer the IMP as described above.
- 6 bottles at Week 6 (Visit 4), Week 12 (Visit 5) and Week 18 (Visit 6) and will self-administer the IMP as described above.

Bottles will be blinded but will contain distinct identification to specify from which bottles the subject should take the capsules.

Table 5

Investigational Medicinal Product Self-Administration

	IMP Bottle					
4 capsules by intake (oral)	Morning placebo	Morning 100 mg	Evening placebo	Evening 100 mg		
Placebo	х		Х			
400 mg OD		Х	Х			
400 mg BID		Х		Х		

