The pharmacokinetics of GKT137831 were consistent in all phase 1 studies. Exposure to GKT137831, measured by mean AUC and  $C_{max}$ , whether after single or repeat administration, increased in a broadly dose proportional manner or less than dose proportional manner. No increased exposure was seen upon single administration of doses higher than 900 mg. After a single dose of 300 mg in either the fasted state or with a non-high fat meal, the mean AUC0-t ranged from 24,100 to 38,000 ng.h/mL. Administration of micronized or unmicronized drug substance did not appear to have any notable impact on plasma exposure. Administration with food appeared to reduce inter-subject variability in exposure, and administration with a high-fat meal increased the mean AUC of GKT137831 by approximately 25%. No reduction in mean exposure was seen upon repeat dosing either at daily doses of 100-900 mg or twice-daily doses of 300-400 mg. A slight accumulation in AUC0-t was measured between the first and last doses upon twice daily dosing, consistent with the increased dosing frequency.

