# 7 STUDY SCHEDULE

The schedule of assessments table is provided in Appendix A. A schedule of blood sampling, including required volumes, is provided in Appendix B. All PD samples are to be collected pre-dose and in fasting condition. Transient elastography must be performed in the morning in fasting condition.

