#### Keys:

1. Day 1 (Visit 2) is also considered baseline of the 24-week double-blind treatment period (except for the determination of the primary endpoint where the mean of Screening (Visit 1) and Day 1 values will be defined as baseline).

2. Eligibility to enter the double-blind treatment period will be determined during Visits 1 and 2. Not every eligibility assessment needs to be repeated at Visit 2 i.e., confirmatory laboratory and diagnostic tests. Subjects with AEs at baseline may need to be withdrawn in accordance with the eligibility and withdrawal criteria.

3. At Screening (Visit 1), a serum pregnancy test will be performed. At all subsequent visits including baseline (Visit 2), urine pregnancy tests will be performed.

- 4. For the Baseline visit and all subsequent visits, subjects must remain fasted overnight from 10 pm and bring their morning dose to the clinic. Pre-dose samples will be collected and subjects will receive a breakfast meal. Subjects will then self-administer the morning dose up to 30 minutes after eating their meal. Post dose samples will be collected as described.
- 5. Post-dose, 12-lead ECG is to be performed around  $T_{max}$ , (i.e. 1 to 4 hours post dose).
- 6. A complete physical examination will be performed during the Screening visit (Visit 1) and at the follow-up (Visit 8). On all other visits a symptoms-directed physical examination will be performed.
- 7. Prior medication will be recorded at Screening only.
- 8. The IMP will be orally self-administered BID, once in the morning and once in the evening with meals or up to 30 minutes after eating a meal.

CONFIDENTIAL

Protocol No.: GSN000300	Compound No.: GKT137831
Protocol Version No.: Final 4.0; Amendment 3	Sponsor: Genkyotex
Protocol Date: 24 July 2018	Author: Cmed Clinical Services

9. PK sampling: one pre-dose PK sample will be collected. Subjects must bring their morning dose to the clinic) and two post-dose samples (first sample to be taken 1-2 hours after morning dose; second sample to be taken before subject leaves clinic but no earlier than 2 hours after the first post-dose sample) at Weeks 2 and 12 (Visits 3 and 5). A single post-dose sample (to be taken before subject leaves clinic at 3-4 hours after morning dose) at Week 18 (Visit 6).

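### Protocol 6.2 is ambiguous about whether the visit-day dose is taken fasted and, on a natural reading, conflicts with the breakfast-then-dose sequence in Appendix A key 4, leaving the prandial state behind the post-dose PK samples and ECGs unsettled

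*Protocol*

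**What the plan says.** Protocol 6.2 sets the everyday rule: the product is taken "with meals or up to 30 minutes after eating a meal". It then turns to visit days, when subjects "should not self-administer the IMP as usual but instead should bring the IMP bottles to the clinic". There the subject is told to "self-administer the morning dose after the required pre-dose blood samplings have been performed, fasted", and the next sentence requires an overnight fast from 10 p.m. No visit-day meal is mentioned.

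Appendix A key 4 covers the same days in more detail. It opens with "For the Baseline visit and all subsequent visits, subjects must remain fasted overnight from 10 pm and bring their morning dose to the clinic", continues with "Pre-dose samples will be collected and subjects will receive a breakfast meal", and then says "Subjects will then self-administer the morning dose up to 30 minutes after eating their meal". Post-dose samples come after that.

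Section 7 ties fasting to sampling: "All PD samples are to be collected pre-dose and in fasting condition". Section 8.2.2 (Table 7), Section 8.1.4 and Appendix A keys 5 and 9 time the PK samples and ECGs from the dose, without stating whether that dose is fed or fasted. SAP 8.8 summarises concentrations by received dose level and planned visit.

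**The concern.** Two passages describe one event, the supervised morning dose at a clinic visit. Read naturally, they put the subject in different prandial states. With approximately 50-60 sites planned, practice could split by whichever page the site staff use.

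The protocol itself gives reason to think food matters. Section 2.1.5.1 reports that "administration with a high-fat meal increased the mean AUC of GKT137831 by approximately 25" percent, and that food appeared to lower the variability of exposure between subjects. Section 3 makes population PK a secondary objective, including inter-individual variability and its predictors, and adds an exploration of PK-PD relationships. If prandial state differs between sites and is not recorded, it becomes an unmeasured source of the variability that the model is meant to explain. The ECGs timed around Tmax would have the same gap in interpretation. Visit-day concentrations could also reflect a different state from the with-meals dosing on all other days.

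**Working it through.** The plan gives no figure to reproduce on this point. The check is a side-by-side reading and a count.

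**1. The two visit-day sequences**

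| Step | Protocol 6.2 | Appendix A key 4 |
|---|---|---|
| Overnight fast | From 10 p.m. | From 10 p.m. |
| Pre-dose bloods | Before the dose | Before the dose |
| Meal | None mentioned | Breakfast, after the bloods |
| Dose | After the bloods, with *fasted* at the end of the sentence | Within 30 minutes after the meal |

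The passages agree on the fast and the sampling. They part at the meal.

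**2. What *fasted* modifies.** The word follows a comma at the end of a clause about both the dose and the bloods. Attached to the dose, it contradicts key 4. Attached to the bloods, it fits key 4 and Section 7. Grammar does not settle it, and the lack of any visit-day meal in 6.2 leaves the first reading at least as natural.

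**3. Which passage governs.** I found no precedence rule. Key 4 is worded for baseline and every later visit, but in the Appendix A table it is attached to the PD-marker rows. The PK row carries key 9 and the ECG row key 5, and neither mentions a meal.

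**4. What is exposed.** From Table 7:
- Week 2: 1 pre-dose + 2 post-dose
- Week 12: 1 pre-dose + 2 post-dose
- Week 18: 1 post-dose
- Total: 3 + 3 + 1 = 7 samples, of which 2 + 2 + 1 = 5 are post-dose and 1 + 1 = 2 are pre-dose

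Appendix B agrees: 6 + 6 + 2 = 14 mL, and 14 / 2 mL per sample = 7. (SAP 5.2 also lists a baseline PK sample, which neither Table 7 nor Appendix B contains; it is not counted here.)

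The visit lists give the Week 2 and Week 12 ECGs explicit post-dose timing. The Week 24 list names only the ECG, so its timing rests on 8.1.4 and key 5. That makes two or three on-treatment ECGs per subject.

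**5. Whether a size can be put on it.** The available inputs are a mean AUC rise of about 25% with a high-fat meal and a single mean AUC range (24,100 to 38,000 ng.h/mL after 300 mg) that pools the fasted state with a non-high-fat meal. Three inputs are missing: the fat content of the breakfast, any food effect on Cmax or Tmax, and the share of visit-day doses that would be taken fasted. The PK samples are also spot concentrations (1-2 hours after the dose, at least 2 hours after that, and 3-4 hours at Week 18), to which an AUC ratio does not carry over. No magnitude can be computed. The lower bound is zero.

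**The case against.** The best defence is that one reading reconciles everything. *Fasted* sits directly after the blood sampling, the next sentence is about the overnight fast, and Section 7 attaches fasting to samples. The with-meals rule stands just above in 6.2 and is repeated in key 8, and key 4 spells out the full order. Section 6.2 omits the visit-day meal; it does not forbid it. The departure from usual practice in "should not self-administer the IMP as usual but instead should bring the IMP bottles to the clinic" concerns bringing the bottles to the clinic, and nothing in it expressly suspends the meal rule.

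Much of this stands. A reader might infer that 6.2 deliberately prescribes fasted dosing as an exception on visit days. The documents do not establish that, and this may be no more than loose wording. But site staff working from 6.2 do not have key 4 in front of them, and the rows for PK and ECG do not lead them to it.

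A second defence is that 6.5 already requires departures from the intended regimen to be recorded in the eCRF. That helps only where the intended regimen is clear. A site following either passage would see nothing to report. The eCRF and the Laboratory Manual are not among the documents, so it cannot be said that meal status goes unrecorded.

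A third is that the 25% figure belongs to a high-fat meal, while key 4 says only breakfast. This is correct. A reader might scale it: if half the visit-day doses were fasted, with a fasted-to-fed ratio of 1/1.25 = 0.80, mean exposure would look 0.5 x 20% = 10% low. The documents do not support that figure. The share is assumed, the meal is unspecified, and the ratio is for AUC.

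**Conclusion.** The concern holds as an ambiguity that conflicts with Appendix A key 4 on a natural reading of 6.2. It reaches 5 of the 7 PK samples per subject and the post-dose ECGs at Weeks 2 and 12, plus Week 24 if 8.1.4 is applied there. Its effect on exposure estimates is unknown and may be nil.

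It would be tempting to extend the point to all PK data or to the efficacy result. The documents do not support either. The two pre-dose samples follow ordinary dosing at home, the screening ECG precedes any dose, and the test, alpha and sample size for GGT do not depend on prandial state.

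The conclusion assumes that some sites would act on 6.2 without consulting key 4, and that no document outside the two reviewed, such as the Laboratory Manual, settles the order. It is more than an editorial matter because the affected data serve stated secondary objectives: population PK, inter-individual variability and its predictors, and safety. It should be corrected, but it does not threaten the trial's main conclusion.

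**What to change.** - Reconcile 6.2 with Appendix A key 4 in one visit-day instruction that covers sampling, meal and dose in order. Which sequence applies is for the sponsor to decide. Cross-reference the instruction from the PK and ECG rows of Appendix A.
- Unless the eCRF already does so, record meal status and meal time with the dose time at the PK visits (Visits 3, 5 and 6) and at any visit with a post-dose ECG. For visits already completed, recover what source records allow.
- Show prandial state in the concentration listings, beside the actual sampling times that SAP 8.8 already lists.
- Name prandial state in the MSAP as a candidate covariate for the population PK model. Both documents have the MSAP finalised before database lock, so this fits the planned timing.

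The cost is a reworded sentence, two cross-references, one small data item, one listing column and one candidate covariate. The sample size and the primary analysis do not change.
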